1 Vitamin D Protocol**2 I. Title**

3 A Triple-Blinded, Randomized Controlled Trial Evaluating Vitamin D₃ Supplementation on
4 Post-Operative Functional and Clinical Outcomes following Total Knee Arthroplasty

5 II. Authors

6 [name], BA; [name]; [name], BA; [name]; [name]
7 J. [name]; [name], MSc.

8 III. Purpose

9 The aim of this study is to determine if the administration of vitamin D₃ on the day of
10 surgery is associated with differences in objective functional outcomes and patient-reported
11 outcome measures in patients undergoing primary total knee arthroplasty compared to patients
12 who do not receive supplementation.

13 IV. Hypothesis

14 Patients undergoing primary total knee arthroplasty who receive vitamin D₃ on the day
15 of surgery prior to procedure will exhibit better functional outcomes measured objectively with
16 functional component of the Knee Society Score (KSS) and a timed up and go (TUG) test at 3
17 and 6 weeks following surgery compared to patients who do not receive vitamin D₃
18 supplementation.

19 V. Background

20 The varied and integral role that Vitamin D plays throughout the body has been well
21 documented with vitamin D receptors having been shown to be present on almost every cell
22 type, and deficiency having been linked to cancer, cardiovascular disease, depression, and many
23 other conditions.^{1,2} Vitamin D is of particular interest with regards to orthopedics for its role in
24 calcium homeostasis, regulating gene transcription in myocytes, and promoting adequate bone
25 mineralization.³

26 Deficiency has been associated with poor post-operative outcomes in patients
27 undergoing total knee arthroplasty. In their analysis of the Humana claims registry that consists
28 of approximately 20 million patients, Hegde et al. found that patients with vitamin D deficiency
29 had higher incidences of manipulation under anesthesia, surgical site infection requiring
30 irrigation and debridement, and prothesis explantation in the year following surgery compared
31 to their vitamin D replete peers after adjusting for age, sex, and Charlson Comorbidity Index
32 (CCI).⁴ In their single center study, Shin et al found that patients with vitamin D deficiency
33 scored lower on the functional component of the KSS score and took longer to complete
34 functional tests at 3 months following surgery compared to their non-deficient peers.⁵ Other
35 studies reported longer length of hospital stay,⁶ lesser improvement in the stiffness component
36 of the Western Ontario and McMaster Universities Osteoarthritis (WOMAC) index,⁷ and greater
37 odds of persistent pain at 3 months following surgery in deficient patients.⁸

38 Although available through dietary sources and skin synthesis in response to ultraviolet
39 B (UVB) exposure, vitamin D deficiency remains one of the most common nutritional
40 deficiencies worldwide, affecting an estimated 1 billion people worldwide and 24 million people
41 (approximately 8%) of Americans.^{9,10} Certain patient populations are at greater risk, and many
42 studies have identified widespread hypovitaminosis D above the national average in patients
43 undergoing orthopedic procedures and arthroplasty.^{3-5, 8, 11-20}

44 Using the Institute of Medicine definition of insufficiency as <30 ng/mL and deficiency
45 as 20 ng/mL,¹⁰ the prevalence of vitamin D deficiency has been reported in studies to range from
46 13 – 61% in patients undergoing total knee arthroplasty (TKA),^{3,4,6,8,21} and 55% in patients
47 undergoing revision THA or TKA.¹² However, even replete patients may become deficient

52 following THA or TKA due to the “surgical stress response,” a series of metabolic, inflammatory,
 53 and endocrine changes that may occur following surgery.^{13, 22, 23} Visser et al. found that vitamin
 54 D levels significantly decreased for patients of all pre-operative levels following THA and
 55 returned to baseline levels for most patients.²² The post-operative decrease in vitamin D, which
 56 ranged from a 25% to 38% decline, was postulated to be secondary to hemodilution; however,
 57 changes in hematocrit concentrations did not correlate with changes in serum vitamin D
 58 concentrations.²² Binkley et al. found a similar significant decrease in vitamin D levels in
 59 patients undergoing THA that was unrelated to changes in fluid balance during the post-
 60 operative period.²³ This postoperative decline in vitamin D levels may negatively impact
 61 functional recovery as vitamin D deficiency has been associated with muscle atrophy in both
 62 animal and human studies.²⁴⁻²⁷

63 Despite the relatively low costs and high success rates of vitamin D supplementation,
 64 there is a dearth of studies evaluating supplementation in patients undergoing TKA. To our
 65 knowledge, only two studies have evaluated prospectively supplementing patients undergoing
 66 TKA. The first study supplemented patients of all pre-operative vitamin D levels 20IU per day
 67 starting 2 weeks after surgery for a duration of four weeks and found no differences in functional
 68 scores assessed with the WOMAC Index, Short-Form Health Survey questionnaire, and KSS at 3
 69 months following surgery.²⁸ However, the dose of supplementation is much lower than any of
 70 the recommended or commonly used doses that use doses of 800 IU or greater for daily
 71 regimens.²⁹ The other study to evaluate supplementation has yet to publish their results, but per
 72 their published protocol, will only supplement patients who are pre-operatively deficient.²
 73 Supplementing only those patients who are pre-operatively deficient presents two limitations as:
 74 [1] previous studies that have demonstrated post-operative declines in vitamin D levels in
 75 patients of all pre-operative levels,^{22, 23} and [2] vitamin D testing is expensive and often not
 76 covered by insurance, limiting the feasibility of institutions to screen pre-operatively.^{29, 30}

77 We propose to fill this knowledge gap by conducting a study that supplements patients
 78 undergoing TKA regardless of pre-operative vitamin D level and with a regimen of 50,000IU
 79 given once that is both proven to be effective and feasible for other clinicians to apply to their
 80 practice.

81

82 **VI. Study Design**

83 Level I: Prospective, randomized controlled trial

84

85 **VII. Inclusion Criteria**

- 86 - Any patient undergoing primary total knee arthroplasty for osteoarthritis
- 87 - Age \geq 18 years old
- 88 - Willingness to undergo randomization and return for all scheduled visits

89

90 **VIII. Exclusion Criteria**

- 91 - Age $>$ 80 years old
- 92 - American Society of Anesthesiologists (ASA) Score \geq 4
- 93 - Other supplemental vitamin D or Calcium use including their analogs: ergocalciferol,
 calcitriol, dihydrotachysterol, and paricalcitol
- 94 - Current cancer
- 95 - Malabsorption syndromes
- 96 - Inability to take medications orally
- 97 - Any reported history of renal disease in stated history (all creatinine, GFR, and other renal-
 related lab values will be abstracted from the clinical record and will not be performed for
 research purposes only)

101 - History of hypercalcemia defined as albumin-corrected hypercalcemia >12 mg/dL (albumin
 102 will be abstracted from the clinical record and will not be performed for research purposes
 103 only)

104 -

105

106 **IX. Demographic/Patient Specific Data Collected**

107 Age, sex, ASA score, height, weight, body mass index, and comorbidities will be collected.

108 **X. Primary Outcome Measure**

109 - Functional component of the 2012 version KSS at time of consenting and at 3 weeks and 6
 110 weeks following surgery

111 **XI. Secondary Outcome Measures**

112 - A timed up and go (TUG) test before surgery at time of consenting and at 3 weeks and 6
 113 weeks following surgery. The TUG test consists of measuring the time it takes for an
 114 individual to rise from a seated position in a chair, walk to a mark 3 meters away, turn
 115 around, come back, and sit in the same chair from which they started. Patients will be asked
 116 to perform the test twice at each of the aforementioned encounters. The use of any assistive
 117 devices such as cane or a walker) will also be noted.

118 - Occurrence of any of the Knee Society's Standardized List of Complications³¹ (Table 1)

119 **XII. Patients and Protocols**

120 Patients will be enrolled from the clinics of [name] and [name] [name], two
 121 fellowship-trained orthopedic surgeons in the division of Adult Reconstruction at Midwest
 122 Orthopedics at Rush University Medical Center. Study staff will screen the clinic schedule of
 123 each surgeon and will discuss the purposes of the investigation at the time of their visit. If the
 124 patient is willing to participate in the investigation, verbal and written consent will be obtained
 125 by the study staff. At the time of consenting, patients will also be asked to perform a TUG test
 126 and will be asked to complete the questions that comprise the functional component of the KSS
 127 score.

128 This study will be tripled-blinded, thus, the patients, clinicians, and research staff
 129 involved will be unaware of patient allocation during this study. Each patient will receive a study
 130 ID, and a computer randomization system will be used to randomize a list of numerical IDs to
 131 either the treatment or control arm. Study IDs will then be written on medication envelopes, and
 132 a member of the clinical team, who is not involved in this study, will then place either the
 133 treatment drug (Vitamin D) or placebo (empty, opaque gelatin capsule) into the envelopes based
 134 on the ID assignment. Only this clinical team member who is not involved in the study will
 135 possess the list matching the study ID to the study group assignment, ensuring that the study
 136 remains triple-blinded and that study coordinators are unaware of a patient's assignment when he
 137 or she picks up the study medication.

138 Patients randomized to the experimental arm of the study will receive 50,000IU of
 139 vitamin D₃ before surgery and asked to take the medication orally before surgery. Vitamin D₃
 140 was selected over vitamin D₂ as the former is less expensive and is more effective at raising
 141 serum 25-OH vitamin D levels than the latter.³² The regimen of 50,000IU given once was
 142 selected as this regimen has been previously used without side effects in previous studies and
 143 has been shown to be as effective as other regimens that utilize more frequent dosing with
 144 smaller doses.^{29, 30, 33} Patients randomized to the control arm will receive placebo tablets of
 145 empty, opaque gelatin capsules and advised to consume their medication similar to the
 146 treatment arm. Both groups of patients will receive their medications from the pharmacy at
 147 Rush Medical Center, which will be responsible for providing patients with the appropriate
 148

151 regimen. All patients will receive the same postoperative multimodal analgesic regimen that is
152 normally administered to patients undergoing THA and TKA at Rush University Medical Center.
153

154 In accordance with current standard post-operative care, patients will be asked to follow-
155 up with their surgeon in clinic at 3 weeks and 6 weeks following surgery. At these post-operative
156 visits, patients will be asked to repeat the TUG test and the 19 questions of the functional
157 component of the KSS score.

158 **XIII. Sample Size**

159 Utilizing data from previous studies, an *a priori* power analysis revealed that 45 patients
160 in each cohort are required to detect a minimally clinically important difference (MCID) of 6
161 points in the functional component of the updated, 2012 KSS version with an assumed standard
162 deviation of 10 points. A difference of 6 points was set as the MCID as that is the value found in
163 a previous study evaluating the previous version of the KSS using patient satisfaction and
164 Oxford Knee Scores as anchors.³⁴ To the best of our knowledge, there are no studies that have
165 quantified the MCID for the 2012 KSS yet. Assuming a 10% drop out rate, we will require 50
166 patients per group for a total of 100 patients overall.

167 **XIV. Treatment and Control Groups**

168 *Numbers reflect an assumed 10% drop out rate

169 Intervention Group: n=50

170 Control Group: n=50

171 **XV. Risks/Benefits**

172 The major risk of patients enrolled in this study stem from potential side effects of
173 hypercalcemia secondary to hypervitaminosis D. Symptoms that have been reported are
174 nausea, dehydration, constipation, polyuria, polydipsia, anorexia, vomiting and muscle
175 weakness. However, documented cases of hypercalcemia due to hypervitaminosis D all involved
176 intake of greater than 40,000IU per day for an extended period of time, and supplementation is
177 widely regarded to be safe in doses under 10,000IU per day for less than 12 weeks^{35, 36}—amounts
178 that are significantly below our proposed dosage. In addition, Binkley et al reported no adverse
179 effects or episodes of toxicity in patients who were supplemented our proposed dosage of
180 50,000IU monthly for one year.³³

181 A risk inherent to every study is the potential for breach of confidentiality and/or
182 privacy. Below is a description of the precautions for maintaining confidentiality.

183 Due to a lack of studies, the benefits of vitamin D supplementation in patients undergoing
184 orthopedic procedures remains unknown. The only study to supplement patients of
185 all vitamin D levels found no differences in functional scores post-operatively among those who
186 did and did not receive supplementation. Based on the many studies demonstrating the negative
187 association between vitamin D deficiency on post-operative outcomes and the benefits of
188 supplementation in patients with knee osteoarthritis, we speculate that supplementation will
189 vitamin D will improve both in patients undergoing total knee arthroplasty with minimal risk of
190 adverse effects.

191 **XVI. Procedures for Maintaining Confidentiality**

192 A breach of confidentiality and/or privacy is a risk of this study. To prevent this, all
193 collected data will be stored electronically in password-protected files to protect patient identity
194 and information. All information will be collected and reviewed by the research team only. Data
195 will be maintained on a password-protected computer that will be accessible only to the study
196 team. No patient identifiers will be maintained in the database.

202
203
204
205
206
207

XVII. Budget

Item	Cost
Vitamin D (50,000IU tablet for 50 patients)	\$17.40
Placebo of Empty, Opaque Gelatin tablets (50 patients)	\$5.69
Total* * All values were provided by the pharmacy at Rush University Medical Center	\$23.09

208
209
210
211
212

213
214**XVIII. Tables and Figures****Table 1 . Knee Society Complication List**

Complication/Adverse Event	Definition
1. Bleeding	Postoperative bleeding requiring surgical treatment
2. Wound complication	Failure of wound healing requiring reoperation or a change in TKA protocol
3. Thromboembolic disease	Symptomatic thromboembolic event requiring more intensive, nonprophylactic anticoagulant or antithrombotic treatment during the first 3 months after index TKA
4. Neural deficit	Postoperative neural deficit (sensory or motor) related to the index TKA
5. Vascular injury	Intraoperative vascular injury requiring surgical repair, bypass grafting, or stenting (compartment syndrome or amputation should be reported)
6. Medial collateral ligament injury	Intraoperative or early postoperative medial collateral ligament injury requiring repair, reconstruction, a change in prosthetic constraint, revision surgery, or TKA protocol
7. Instability	Symptomatic instability reported by the patient and confirmed by laxity on physical examination as defined by The Knee Society Knee Score
8. Misalignment	Symptomatic malalignment reported by the patient and confirmed radiographically with angular deformity in the coronal plane [10° from the mechanical axis]
9. Stiffness	Limited ROM as reported by the patient and demonstrated in a physical examination with extension limited to 15° short of full extension or flexion $< 90^\circ$ (not applicable if preoperative arc of motion $< 75^\circ$)
10. Deep periprosthetic joint infection	A deep periprosthetic joint infection can be diagnosed when there is a sinus tract communicating with the prosthesis; or a pathogen is isolated by culture from at least two separate tissue or fluid samples obtained from the affected prosthetic joint; or 4 of the following 6 criteria exist: elevated ESR and serum CRP concentration; elevated synovial WBC count; elevated synovial PMN; presence of purulence in the affected joint; isolation of a microorganism in one culture of periprosthetic tissue or fluid; or >5 neutrophils/high-power field in 5 high-power fields observed from histologic analysis of periprosthetic tissue at 9400 magnification
11. Periprosthetic fracture	Periprosthetic fracture of the distal femur, proximal tibia, or patella (operative or nonoperative treatment should be recorded).
12. Extensor Mechanism Disruption	Disruption of the extensor mechanism (surgical repair and/or extensor lag should be recorded)
13. Patellofemoral dislocation	Dislocation of the patella from the femoral trochlea (direction of instability should be recorded)
14. Tibiofemoral dislocation	Dislocation of the tibiofemoral joint (direction of instability should be recorded)
15. Bearing surface wear	Wear of the bearing surface symptomatic or requiring reoperation
16. Osteolysis	Expansile lytic lesion adjacent to one of the implants 1 cm in any one dimension or increasing in size on serial radiographs/CT scans

17. Implant loosening	Implant loosening confirmed intraoperatively or identified radiographically as a change in implant position or a progressive, radiolucent line at the bone-cement or bone-implant interface
18. Implant fracture or tibial insert dislocation	Implant fracture or dissociation of the tibial insert from the tibial implant
19. Reoperation	Return to the operating room related to the index TKA (reasons for reoperation should be recorded)
20. Revision	Revision of one or more of the TKA implants (femur, tibia, tibial insert, patella)
21. Readmission	Admission to the hospital for any reason during the first 90 days after TKA (reasons for admission and relation to index TKA should be recorded)
22. Death	Death occurring for any reason during the first 90 days after TKA (cause of death and relation to index TKA should be recorded)

215

216

217

218 **XIX. References**

219 1. Wacker M, Holick M. Vitamin D—effects on skeletal and extraskeletal health and the need for
220 supplementation. *Nutrients*. 2013;5(1):111-48.

221 2. Morrison RJM, Bunn D, Gray WK, Baker PN, White C, Rangan A, et al. VASO (Vitamin D and
222 Arthroplasty Surgery Outcomes) study - supplementation of vitamin D deficiency to improve outcomes
223 after total hip or knee replacement: study protocol for a randomised controlled feasibility trial. *Trials*.
224 2017 Nov 2;18(1):514. Epub 2017/11/04.

225 3. Piuazzi NS, George J, Khlopas A, Klika AK, Mont MA, Muschler GF, et al. High prevalence and
226 seasonal variation of hypovitaminosis D in patients scheduled for lower extremity total joint arthroplasty.
227 *Ann Transl Med*. 2018 Aug;6(16):321. Epub 2018/10/27.

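### Does the Table 1 complication outcome need a stated data source, a common time window and a listed preoperative arc of motion?

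*Combined protocol and SAP*

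**What the plan says.** Section XI gives the complication outcome in one line, "Occurrence of any of the Knee Society" and so on, with a pointer to Table 1 and no assessment time, source or assessor. The outcomes around it are fuller. Section X sets the primary outcome as "Functional component of the 2012 version KSS at time of consenting and at 3 weeks and 6" weeks after surgery, and the TUG entry in Section XI gives times and a procedure.

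Section XII places follow-up with the surgeon at 3 and 6 weeks. At those "visits, patients will be asked to repeat the TUG test and the 19 questions of the functional" part of the KSS; complications are not mentioned there.

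Table 1 puts a 3-month window on thromboembolic disease (item 3) and a 90-day window on readmission and death (items 21 and 22). Vascular injury (item 5) is intraoperative. Ligament injury (item 6) is intraoperative or early postoperative, with early left undefined. Stiffness (item 9) reads "Limited ROM as reported by the patient and demonstrated in a physical examination with extension limited to" 15° short of full, or flexion below 90°, and is "not applicable if preoperative arc of motion" was under 75°. Instability (item 7) must be "confirmed by laxity on physical examination as defined by The Knee Society Knee Score".

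Section IX, on demographic and patient-specific data, says "Age, sex, ASA score, height, weight, body mass index, and comorbidities will be collected". Abstraction from the clinical record is mentioned only in Section VIII, for renal values and albumin.

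**The concern.** An outcome counted as any event from a list needs a time horizon. Without one, a single record review on one calendar date would follow early enrolees longer than late ones, and the resulting proportion would not be the risk at any stated time. The three windows that Table 1 does give run past the last described visit, so stopping collection at 6 weeks would cut them short.

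The stiffness item looks worse, because it turns on a preoperative measurement that cannot be taken after surgery. If nobody recorded it, the same postoperative knee could be a complication or outside the definition, with no way to tell which. Instability raises a similar doubt, since it refers to the Knee Society Knee Score while the study collects only the functional component. Items such as item 8, "Symptomatic malalignment reported by the patient and confirmed radiographically", also need findings that no section says will be gathered. At stake is whether this secondary outcome can be scored in the same way for all 100 planned patients.

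**Working it through.** The plan gives no figure to reproduce here. The check is a count of Table 1 and a side-by-side reading of the sections.

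**Time windows**

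- Items in Table 1: 22.
- With a calendar window (3, 21, 22): 3, leaving 22 − 3 = 19.
- Bounded by the operation (5): 1, leaving 19 − 1 = 18.
- Limited to an undefined early period (6): 1, leaving 18 − 1 = 17 with no end point at all.

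The count is therefore 17, 18 or 19 of 22, depending on how items 5 and 6 are treated. The gap is real on any of these readings.

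**Overhang past the last visit**

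- Six weeks is day 42. For items 21 and 22, 90 − 42 = 48 days lie after it.
- For item 3, taking 3 months as 91 to 92 days, 49 to 50 days lie after it.

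This is follow-up time, not events. The plan neither describes nor excludes later collection, so no loss can be inferred.

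**Stiffness (item 9)**

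The definition has three parts: (a) the patient reports limited motion; (b) examination shows the stated limit in extension or flexion; (c) the preoperative arc was not under 75°. An event requires all three.

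| (a) reported | (b) found on examination | Is (c) needed? |
|---|---|---|
| no | either | no: not an event |
| yes | no | no: not an event |
| yes | yes | yes |

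The preoperative value decides only the last row. Everyone else can be classified without it.

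**Is Section IX a full data list?**

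It omits the KSS, the TUG and the use of assistive devices, all of which Sections X and XI say are recorded. Absence from Section IX therefore does not show that a value will go uncollected. The remarks in Section VIII explain that laboratory tests will not be done for research alone; they do not restrict other use of the record.

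**Instability (item 7)**

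The Knee Score is cited there to define laxity on examination. The item does not require that component to be a study score, and an examination at a surgeon's visit can meet it.

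**Effect on the comparison**

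Section XII allocates patients from a computer-randomised list and keeps patients, clinicians and research staff unaware of the arm. Unequal follow-up by enrolment date would then fall on both arms alike in expectation. It would blur what the proportion means without favouring either arm.

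**The case for a change.** The strongest case for a change is that the repair is cheap and part of it is time-critical. One sentence would fix source and window, and one baseline field would secure the arc of motion, which cannot be measured once surgery has been done. Reading 6 weeks as the implied cut-off is not fully satisfactory either: no section ties complications to that visit, and it would conflict with the windows in items 3, 21 and 22. A published list supplies definitions, but the trial still has to supply the horizon. Stiffness is also close to the trial's own rationale, since the Background cites less improvement on a stiffness scale in deficient patients.

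The facts in this argument stand, and a clarifying sentence would do no harm. The need for it is weaker. The calendar-date review is a supposition; no section plans one. The hypothesis, the primary outcome, the TUG and the visits all run to 6 weeks, which gives staff a natural default for items without a window, while items 3, 21 and 22 carry their own. Adding a common window would not by itself give one clean risk: with 6 weeks for the open items and 90 days or 3 months for the others, any-complication would still mix horizons. The documents also offer no basis for preferring one window, so the choice would fall to the sponsor in any case.

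**Conclusion.** No change follows. Section XI is short on operational detail for a secondary outcome: 17 of the 22 items have no end point (18 if the undefined early period in item 6 is not counted as one), three windows extend 48 to 50 days past the last described visit, and the preoperative arc of motion is not listed. Staff applying Table 1 at routine surgeon visits and from the clinical record would fill these gaps sensibly, and a report of complications can state the window used.

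The documents show no bias between arms and no lost events, and neither the hypothesis nor the sample size rests on complications. The conclusion assumes that the clinical record holds the examination findings, including preoperative motion for the few patients in whom it decides the stiffness item, and that any window is settled while staff remain blinded. The documents neither confirm nor contradict the first assumption; the blinding described in Section XII supports the second.

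### Functional KSS and TUG are measured at consent, but the plan gives these baselines no role and does not say what the SD of 10 describes; baseline adjustment should be pre-specified

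*Combined protocol and SAP*

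**What the plan says.** Section X defines the primary outcome as "Functional component of the 2012 version KSS at time of consenting and at 3 weeks and 6" weeks after surgery, so the pre-treatment value and two follow-up values stand together in one entry. Section XI does the same for the main secondary outcome: "A timed up and go (TUG) test before surgery at time of consenting and at 3 weeks and 6" weeks. Section XII confirms that both are done at consent; for the score, patients perform the TUG "and will be asked to complete the questions that comprise the functional component of the KSS".

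The nearest thing to an analysis contrast is Section IV, which expects better results in the vitamin D arm on the "functional component of the Knee Society Score (KSS) and a timed up and go (TUG) test at 3" and 6 weeks. It mentions neither baseline nor change.

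Section XIII is the only quantitative basis. It reports that a "power analysis revealed that 45 patients" "in each cohort are required to detect a minimally clinically important difference (MCID) of 6" points, with an assumed standard "deviation of 10 points. A difference of 6 points was set as the MCID". It ties the SD to no visit, to no change and to no adjusted analysis. The headings run from I to XIX without a statistical analysis section, and no test, model, covariate or change-score definition appears under any of them.

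**The concern.** A baseline measurement of the primary outcome is usually collected so that it can be used. Here the plan is silent. It does not choose an unadjusted analysis; it leaves three analyses available, and Section X can be read as supporting any of them.

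An unadjusted comparison of randomised arms is valid, so no bias is alleged. Two other things are at stake. First, the three analyses have different power for the same 45 patients per arm, and the ordering of the two unadjusted ones depends on a correlation and an SD definition that the plan does not give. Second, an estimator that is not fixed in advance can be chosen once the arms have been compared. The triple blinding in Section XII does not prevent this, because it ends before the results are read.

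**Working it through.** **Inputs.** Difference 6 points, SD 10 and 45 evaluable patients per arm, all from Section XIII. Significance level and power are not stated; two-sided 5% is assumed. The baseline-to-follow-up correlation r is not in the documents, so a range is used.

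**Reproducing the plan's figure.** For a two-sample t-test the noncentrality is 6 / (SD × √(2/n)). With SD 10 and n = 45 this is 6 / (10 × 0.2108) = 2.846 on 88 degrees of freedom, which gives 80.4% power. Solving for 80% power gives 44.59, so 45 per arm, and 45 / 0.9 = 50 with dropout. The sample size is thus that of a plain two-sample t-test with no baseline term.

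**SD under each analysis.** Let S be the follow-up SD.

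- Follow-up score only: S.
- Baseline-adjusted linear model (ANCOVA): S√(1 − r²), with 87 degrees of freedom.
- Change score, equal SDs at both visits: S√(2(1 − r)).

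The SD of 10 can be read in three ways: (i) follow-up SD, S = 10; (ii) change SD, S = 10/√(2(1 − r)); (iii) residual SD, S = 10/√(1 − r²). Each cell gives the SD and then the power at 45 per arm, with equal SDs at both visits for reading (ii) and for the change score.

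| Reading of SD 10 | r | ANCOVA | Follow-up only | Change score |
|---|---|---|---|---|
| (i) follow-up | 0.3 | 9.54, 83.9% | 10.00, 80.4% | 11.83, 66.2% |
| | 0.5 | 8.66, 90.1% | 10.00, 80.4% | 10.00, 80.4% |
| | 0.6 | 8.00, 94.0% | 10.00, 80.4% | 8.94, 88.2% |
| (ii) change | 0.3 | 8.06, 93.7% | 8.45, 91.5% | 10.00, 80.4% |
| | 0.5 | 8.66, 90.1% | 10.00, 80.4% | 10.00, 80.4% |
| | 0.6 | 8.94, 88.2% | 11.18, 71.1% | 10.00, 80.4% |
| (iii) residual | 0.3 | 10.00, 80.4% | 10.48, 76.6% | 12.40, 62.2% |
| | 0.5 | 10.00, 80.4% | 11.55, 68.4% | 11.55, 68.4% |

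**Low correlation.** Under (i), ANCOVA has 80.4% power at r = 0 and 81.9% at r = 0.2, so the gain is negligible there. The cost at r = 0 is one degree of freedom: 80.37% becomes 80.36%.

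**Unequal SDs.** Under (i) with r = 0.3 and baseline SD b, the change-score SD is √(100 + b² − 6b). For b = 6, 8, 10 and 12 this is 10.0, 10.77, 11.83 and 13.11, with power 80%, 74%, 66% and 57%. In general the change score loses to the follow-up score when r < b/20.

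**Why ANCOVA holds up.** The model chooses the baseline slope that minimises residual variance. Follow-up-only fixes that slope at 0 and the change score fixes it at 1, so the ANCOVA residual SD cannot exceed either of theirs. If 10 is any one of the three SDs, the residual SD is at most 10 and power is about 80% or more, whatever r is.

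**Simulation check** under (i), 20,000 trials per value of r: ANCOVA power 80.2%, 83.7%, 89.9% and 94.1% at r = 0, 0.3, 0.5 and 0.6, against 80.5% to 80.9% unadjusted.

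**The case against.** The strongest reply is that the hypothesis contrasts the arms at 3 and 6 weeks and that 45 per arm is exactly a two-sample t-test, so reading (i) is the natural one. On that reading the follow-up comparison has 80.4% power at every r and nothing is lost. Reading (iii) has no direct support, since the protocol never mentions adjustment. This carries weight: the three readings are not equally likely, and the low follow-up-only figures arise only under (ii) with r above 0.5 or under (iii). But the text does not settle the reading, and even under (i) adjustment costs practically nothing and may gain.

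The change score is also not always poor. Under (i) it reaches 80.4% at r = 0.5 and 88.2% at r = 0.6, and under (ii) it stays at 80.4%. That is correct. It still never beats ANCOVA by more than the trivial effect of one degree of freedom.

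That ANCOVA is never materially worse is an algebraic fact about any trial with a baseline, not evidence of an error here. Agreed; it is a reason to prefer the method, and the silence of the plan is the reason to raise it.

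Finally, the gap is part of a larger one. Significance level, power, test and primary time point are also unstated, and Section XI has TUG performed twice per visit with no rule for combining the attempts. All of this stands. It means that fixing baseline handling will not alone close the analysis plan, and that the power figures cover KSS only, as no TUG SD is given.

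**Conclusion.** The concern holds. The consent-visit functional KSS and TUG have no stated role in the comparison, and the SD of 10 is undefined. The sample size is not wrong and an unadjusted analysis would be valid. The point is that baseline adjustment alone keeps about 80% power or more under every reading of the SD, while follow-up-only falls to between 68% and 77% and change score to between 57% and 74% in the unfavourable cases shown. The exact figures rest on assumed correlations, a two-sided 5% level and, for some entries, equal SDs at the two visits. The benefit may be negligible if r is low. This should be changed before the arms are compared, but it does not threaten the trial's validity. The unlabelled SD would on its own be a minor clarification.

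**What to change.** State that the primary analysis is a linear model of follow-up functional KSS on randomised arm, with consent-visit functional KSS as covariate, and that TUG is analysed in the same way with consent-visit TUG. Say in Section XIII whether 10 is a follow-up, change or residual SD. Before the TUG model can be applied, the plan also needs a rule that turns the two attempts at each visit into one value.

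The 45 evaluable per arm (50 with dropout) can stay: it is about right if 10 is a residual SD and at least sufficient if it is a follow-up or change SD, with a margin that depends on r. A repeated-measures model over weeks 3 and 6 with the same covariate is optional. Which visit is primary is a separate decision that this change does not make.

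The cost is one or two sentences on the model and the SD, a line for the TUG rule, and one extra model term. No additional patients, visits or measurements are needed, and the power lost if baseline proves uninformative is about 0.01 percentage points.
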